10.4.3. Safety Analyses

Safety analyses will be conducted for the safety population. Adverse events will be coded by the MedDRA dictionary, and TEAEs (ie, AEs reported for the first time or worsening of a pre-existing event after first dose of study drug/treatment) will be tabulated by preferred term and system organ class for all events, related events, and events of Grade 3 or higher. Quantitative safety variables and their changes from baseline (laboratory, vital signs, etc) will be summarized with descriptive statistics. Clinically notable abnormal values will be flagged and tabulated based on predefined criteria.

Clinical laboratory data will be analyzed using summary statistics; no formal treatment group comparisons are planned. In addition, distributions of key laboratory parameters may be plotted over time; these values will also be classified into CTCAE v4.03 toxicity grades and tabulated. Descriptive statistics and mean change from baseline will be determined for vital signs at each assessment time. Vital sign results will be reviewed for clinically notable abnormalities.

Measures of exposure (eg, days of exposure, dose intensity, etc) of study drug and reference therapy will be summarized by means of summary statistics.

In order to accommodate the changes proposed in Protocol Amendment 8 that resulted in discontinuation of Treatment Group C (300 mg BID) and subsequent dose reduction of on-going participants in Treatment Group C to 400 mg QD, safety tables (specifically AEs) will be presented for the 300 mg BID group with participants who are subject to dose reduction and censored at the date of switching to the lower dose (400 mg QD). In addition, an overall summary including both dose groups (participants included before and after the dose reduction) will also be presented.

10.4.4. Pharmacokinetic Analyses

In participants with full profiles, that is, in Part 1, Part 1 expansion, or Part 2 before the IA, the PK parameters of C_{max}, T_{max}, C_{min}, AUC_{0-t}, and Cl/F will be calculated from the blood plasma concentrations of itacitinib using standard noncompartmental (model-independent) PK methods. Pharmacokinetic calculations will be performed using commercial software such as WinNonlin® (Pharsight Corporation, Mountain View, CA). Predose concentrations at Day 7 and Day 28 will be summarized for participants in Part 2 after the IA.

10.5. Interim Analysis

An interim analysis for futility will be performed once 70 participants (35 per arm) have completed the Day 180 visit; the final analysis will be performed once all participants have completed the Day 180 visit.

A group sequential design method for 2-sample binary outcome data was used to calculate the lower futility boundary for the interim analysis with an HSD(-4) spending function. The study will be stopped for futility if the test statistic z is less than -0.87. In the final analysis, if the test statistics z is ≥ 1.96 , then the superiority of itacitinib plus corticosteroids over placebo plus corticosteroids will be claimed.

Preplanned analyses of safety (Part 1, Part 1 expansion, and Part 2) and efficacy (Part 1 expansion and Part 2) will be provided to an independent DMC as specified in the DMC charter. The process by which the DMC will review data and make recommendations and decisions will be documented in the DMC charter.

11. SUPPORTING DOCUMENTATION AND OPERATIONAL CONSIDERATIONS

11.1. Investigator Responsibilities

- The Protocol, Protocol amendments, ICF, IB, and other relevant documents (eg, advertisements) must be submitted to an IRB/IEC by the investigator and reviewed and approved by the IRB/IEC before the study is initiated.
- The investigator is responsible for ensuring that the safety reports provided by the sponsor are reviewed and processed in accordance with regulatory requirements, the policies and procedures established by the IRB/IEC, and institutional requirements.
- Any amendments to the Protocol will require IRB/IEC approval before implementation of changes made to the study design, except for changes necessary to eliminate an immediate hazard to study participants.
- The investigator will be responsible for the following:
 - Providing written summaries of the status of the study to the IRB/IEC annually or more frequently in accordance with the requirements, policies, and procedures established by the IRB/IEC.
 - Notifying the IRB/IEC of SAEs or other significant safety findings as required by IRB/IEC procedures.
 - Providing oversight of the conduct of the study at the site and adherence to GCP, IRB/IEC requirements, institutional requirements, and applicable laws and country-specific regulations.
- Adhering to the Protocol as described in this document and agreeing that changes to the Protocol procedures, with the exception of medical emergencies, must be discussed and approved, first, by the sponsor or its designee and, second, by the IRB/IEC. Each investigator is responsible for enrolling participants who have met the specified eligibility criteria.

- Retaining records in accordance with all local, national, and regulatory laws, but for a minimum period of at least 2 years after the last marketing application approval in an ICH region and until there are no pending or contemplated marketing applications in an ICH region, or if not approved, 2 years after the termination of the test article for investigation to ensure the availability of study documentation should it become necessary for the sponsor or a regulatory authority to review.
 - The investigator must not destroy any records associated with the study without receiving approval from the sponsor. The investigator must notify the sponsor or its designee in the event of accidental loss or destruction of any study records. If the investigator leaves the institution where the study was conducted, the sponsor or its designee must be contacted to arrange alternative record storage options.
 - All eCRF data entered by the site (including audit trail), as well as computer hardware and software (for accessing the data), will be maintained or made available at the site in compliance with applicable record retention regulations. The sponsor will retain the original eCRF data and audit trail.

11.2. Data Management

Data management will be performed in a validated EDC system. The investigator will be provided with access to an EDC system so that an eCRF can be completed for each participant.

The site will be provided eCRF completion guidelines for instructions on data entry in the eCRF. The study monitor will reference the Monitoring Plan in order to ensure that each issue identified is appropriately documented, reported, and resolved in a timely manner in accordance with the plan's requirements.

The sponsor (or designee) will be responsible for:

- The data management of this study including quality checking of the data.
- Ensuring that study monitors perform ongoing source data verification to confirm that
 data entered into the eCRF by authorized site personnel are accurate, complete, and
 verifiable from source documents; that the safety and rights of participants are being
 protected; and that the study is being conducted in accordance with the currently
 approved protocol and any other study agreements, ICH GCP, and all applicable
 regulatory requirements.

The investigator will be responsible for:

• Ensuring participant data relating to the study is recorded in the eCRF unless transmitted to the sponsor or designee electronically (eg, laboratory data, diary data) or as otherwise specified in the Protocol. The investigator is responsible for verifying that data entries are accurate and correct by physically or electronically signing the eCRF.

- Maintaining accurate documentation (source data) that supports the information entered in the eCRF.
 - Source documents provide evidence for the existence of the participant and substantiate the integrity of the data collected. Source documents are filed at the investigator's site.
 - Data reported on the CRF or entered in the eCRF that are transcribed from source documents must be consistent with the source documents or the discrepancies must be explained. The investigator may need to request previous medical records or transfer records, depending on the study. Also, current medical records must be available.
- Permitting study-related monitoring, sponsor audits, IRB/IEC review, and regulatory inspections by providing direct access to source data and other relevant clinical study documents.
 - Monitoring: Qualified representatives of the sponsor or its designee, study
 monitors, will monitor the study according to a predetermined plan. The
 investigator must allow the study monitors to review any study materials and
 participant records at each monitoring visit.
 - Auditing: Qualified representatives of the sponsor or its designee may audit the clinical study site and study data to evaluate compliance with the Protocol, applicable local clinical study regulations, and overall study conduct. The investigator must allow the auditors to review original source records and study documentation for all participants.
 - Regulatory inspection: Regulatory authorities may conduct an inspection of the study and the site at any time during the development of an investigational product. The investigator and staff are expected to cooperate with the inspectors and allow access to all source documents supporting the eCRFs and other study-related documents. The investigator must immediately notify the sponsor when contacted by any regulatory authority for the purposes of conducting an inspection.

11.3. Data Privacy and Confidentiality of Study Records

The investigator and the sponsor or its designee must adhere to applicable data privacy laws and regulations. The investigator and the sponsor or its designee are responsible for ensuring that sensitive information is handled in accordance with local requirements (eg, HIPAA). Appropriate consent and authorizations for use and disclosure and/or transfer (if applicable) of protected information must be obtained.

Participant names will not be supplied to the sponsor or its designee. Only the participant number will be recorded in the eCRF; if the participant's name appears on any other document (eg, laboratory report), it must be obliterated on the copy of the document to be supplied to the sponsor or its designee. Study findings stored on a computer will be stored in accordance with local data protection laws.

11.4. Financial Disclosure

Before study initiation, all clinical investigators participating in clinical studies participant to FDA Regulation Title 21 CFR Part 54 – Financial Disclosure by Clinical Investigators (ie, "covered studies") are required to submit a completed Clinical Investigator Financial Disclosure form that sufficiently details any financial interests and arrangements that apply. For the purpose of this regulation, "clinical investigator" is defined as any investigator or subinvestigator who is directly involved in the treatment or evaluation of research participants, including the spouse and each dependent child of the clinical investigator or subinvestigator. These requirements apply to both US and foreign clinical investigators conducting covered clinical studies.

Any new clinical investigators added to the covered clinical study during its conduct must also submit a completed Investigator Financial Disclosure Form. During a covered clinical study, any changes to the financial information previously reported by a clinical investigator must be reported to the sponsor or its designee. At the conclusion of the covered clinical study, the clinical investigators will be reminded of their obligations. In the event that the clinical investigator is not reminded, they nevertheless will remain obligated to report to the sponsor or its designee any changes to the financial information previously reported, as well as any changes in their financial information for a period of 1 year after completion of the covered clinical study.

11.5. Publication Policy

By signing the study Protocol, the investigator and his/her institution agree that the results of the study may be used by the sponsor, Incyte Corporation (Incyte), for the purposes of national and international registration, publication, and information for medical and pharmaceutical professionals. Study results will be published in accordance with applicable local and national regulations. If necessary, the authorities will be notified of the investigator's name, address, qualifications, and extent of involvement. The terms regarding the publication of study results are contained in the agreement signed with the sponsor or its designee. A signed agreement will be retained by the sponsor or its designee.

The results of this study may be published or presented at scientific meetings. If this is foreseen, the investigator agrees to submit all manuscripts or abstracts to the sponsor before submission. This allows the sponsor to protect proprietary information and to provide comments.

The sponsor will comply with the requirements for publication of study results. In accordance with standard editorial and ethical practice, the sponsor will generally support publication of multicenter studies only in their entirety and not as individual site data. In this case, a coordinating investigator will be designated by mutual agreement.

Authorship will be determined in line with International Committee of Medical Journal Editors authorship requirements.

11.6. Study and Site Closure

The sponsor designee reserves the right to close the study site or terminate the study at any time for any reason at the sole discretion of the sponsor. Study sites will be closed upon study completion. A study site is considered closed when all required documents and study supplies have been collected and a study-site closure visit has been performed.

The investigator may initiate study-site closure at any time, provided there is reasonable cause and sufficient notice is given in advance of the intended termination.

Reasons for the early closure of a study site by the sponsor or investigator may include but are not limited to:

- Failure of the investigator to comply with the protocol, the requirements of the IRB/IEC or local health authorities, the sponsor's procedures, or GCP guidelines.
- Inadequate recruitment of participants by the investigator.
- Discontinuation of further study treatment development.

APPENDIX A. INFORMATION REGARDING EFFECTIVENESS OF CONTRACEPTIVE METHODS

For male participants in the study:

Male participants should use a condom during treatment and through 90 days after the end of systemic exposure. If the male participant has a partner that is of child-bearing potential, the partner should also use contraception through 90 days after the end of relevant systemic exposure. In addition, male participants must refrain from donating sperm during the study through 90 days after the end of relevant systemic exposure. Males who have had a vasectomy qualify as having met the requirement for a highly effective birth control method.

For female participants in the study:

The following methods that can achieve a failure rate of less than 1% per year when used consistently and correctly are considered as highly effective birth control methods.

Such methods include:

- Combined (estrogen and progestogen containing) hormonal contraception associated with inhibition of ovulation¹
 - oral
 - intravaginal
 - transdermal
- Progestogen-only hormonal contraception associated with inhibition of ovulation¹
 - oral
 - injectable
 - implantable²
- Intrauterine device (IUD)²
- Intrauterine hormone-releasing system (IUS)²
- Bilateral tubal occlusion²
- Vasectomised partner^{2,3}
- Sexual abstinence⁴

Acceptable birth control methods that result in a failure rate of more than 1% per year include:

- progestogen-only oral hormonal contraception, where inhibition of ovulation is not the primary mode of action
- male or female condom with or without spermicide⁵
- cap, diaphragm or sponge with spermicide⁵
- tubal ligation

For participants in the study in Canada:

In order to conform to Health Canada guidance⁶, participants in this clinical study in Canada are to use 2 forms of contraception, including at least 1 form of highly effective and 1 effective method of contraception. Participants who are using combined hormonal contraception or progestogen-only hormonal contraception will be required to include a barrier method as well.

¹ Hormonal contraception may be susceptible to interaction with the IMP, which may reduce the efficacy of the contraception method

² Contraception methods that in the context of this guidance are considered to have low user dependency.

- ³ Vasectomised partner is a highly effective method of avoiding pregnancy provided that partner is the sole sexual partner of the WOCBP trial participant and that the vasectomised partner has received medical assessment of the surgical success.
- ⁴ In the context of this guidance, sexual abstinence is considered a highly effective method only if defined as refraining from heterosexual intercourse during the entire period of risk associated with the study treatments. The reliability of sexual abstinence needs to be evaluated in relation to the duration of the clinical trial and the preferred and usual lifestyle of the participant.
- ⁵ A combination of male condom with either cap, diaphragm or sponge with spermicide (double barrier methods) are also considered acceptable, but not highly effective, birth control methods.
- ⁶ http://www.hc-sc.gc.ca/dhp-mps/prodpharma/applic-demande/guide-ld/clini/womct_femec-eng.php (accessed May 28, 2019). Source: Clinical Trial Facilitation Group 2014.

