5.1. Inclusion Criteria

Participants are eligible to be included in the study only if all of the following criteria apply:

- 1. Male or female, aged 18 years or older inclusive at the time of signing the ICF.
- 2. Active, clinically diagnosed, moderate or severe cGVHD per NIH Consensus Criteria (Jagasia et al 2015; Appendix C):
 - a. Moderate cGVHD: At least 1 organ (except lung) with a score of 2, 3 or more organs involved with a score of 1 in each organ, or lung score of 1.
 - b. Severe cGVHD: At least 1 organ with a score of 3, or lung score of 2 or 3.

Note: Candidates who transition from active aGVHD to cGVHD without tapering off of corticosteroids (< 0.25 mg/kg per day methylprednisolone or equivalent) \pm CNI are also eligible.

- 3. Underwent allo-HCT from any donor HLA type (related or unrelated donor with any degree of HLA matching) using any graft source (bone marrow, peripheral blood stem cells, or cord blood). Recipients of myeloablative, nonmyeloablative, or reduced intensity conditioning are eligible.
- 4. KPS score $\geq 60\%$.
- 5. Evidence of myeloid and platelet engraftment, that is, ANC $\geq 1.0 \times 10^9/L$ and platelet count $\geq 50 \times 10^9/L$. *Note:* Use of growth factor supplementation and transfusion support is allowed during the study; however, transfusion to reach a minimum platelet count for inclusion is not allowed within the 7 days before the screening laboratory assessment.
- 6. Willingness to avoid pregnancy or fathering children based on the criteria below.
 - a. Men must agree to take appropriate precautions to avoid fathering children (with at least 99% certainty) from screening through 90 days after the last dose of study drug(s)/treatment and must refrain from donating sperm during this period. Permitted methods that are at least 99% effective in preventing pregnancy (see Appendix A) should be communicated to the participants and their understanding confirmed.
 - b. Women of childbearing potential must have a negative serum pregnancy test at screening and before the first dose on Day 1 and must agree to take appropriate precautions to avoid pregnancy (with at least 99% certainty) from screening through safety follow-up. Permitted methods that are at least 99% effective in preventing pregnancy (see Appendix A) should be communicated to the participants and their understanding confirmed.

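### Outside Canada, Appendix A sets no effectiveness level for contraception by the partner of a non-vasectomised man, although criterion 6a requires 99% certainty and sends sites there for methods

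*Protocol*

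**What the plan says.** Protocol Section 5.1, criterion 6a, sets the level and the period for men, with the 90 days counted from the last dose: "Men must agree to take appropriate precautions to avoid fathering children (with at least 99% certainty) from screening through 90 days". It then refers sites to the appendix: "Permitted methods that are at least 99% effective in preventing pregnancy (see Appendix A) should be communicated to the participants".

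The paragraph for male participants in Appendix A gives these contraception instructions:

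- For the man: "Male participants should use a condom during treatment and through 90 days after the end of systemic exposure".
- For the partner, with the 90 days counted from when relevant systemic exposure ends: "If the male participant has a partner that is of child-bearing potential, the partner should also use contraception through 90 days". Neither a level nor a start is given.
- For vasectomy: "Males who have had a vasectomy qualify as having met the requirement for a highly effective birth control method".

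Later in the appendix, under the heading for female participants, methods are split into two lists. The first holds methods with a failure rate below 1% per year, called highly effective. The second opens: "Acceptable birth control methods that result in a failure rate of more than 1% per year include". The condom is on this second list: "male or female condom with or without spermicide". Footnote 5 deals with a male condom combined with a cap, diaphragm or sponge with spermicide, and classes such pairings as follows: "double barrier methods) are also considered acceptable, but not highly effective, birth control methods".

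A separate paragraph for Canada requires two forms of contraception, at least one of them highly effective.

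**The concern.** Criterion 6a leaves the choice of method to Appendix A. If the appendix can be followed to the letter by a couple who fall short of 6a, sites may counsel couples differently and reach different eligibility decisions. Section 5 of the protocol allows no eligibility waivers.

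The wording matters more for men than for women because men have no second safeguard. A female participant of childbearing potential has a negative serum test at screening and before the first dose (criterion 6b), then a test every 28 days (Section 8.3.8.3 and Table 21), and study drug is stopped if she becomes pregnant (Sections 7.1.1 and 9.7). The partner of a male participant is not tested, and Section 9.7 restricts immediate discontinuation to female participants. After a partner pregnancy, only reporting and follow-up of the outcome remain. The contraception instruction is thus the only preventive measure against paternal exposure.

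**Working it through.** The plan states no figure that could be reproduced. The check is a comparison of the texts, plus two short sums that limit what the timing can mean.

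**Level**

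1. Criterion 6a requires at least 99% certainty. Read on the appendix's yearly scale, that means a failure rate of about 1% per year or less, which is the appendix's border between highly effective methods and the rest. Criterion 6a names no time basis, so using the yearly scale is an assumption. It is the natural one, because 6a itself points to this appendix.
2. The male paragraph names two measures for a non-vasectomised man with a partner of child-bearing potential: a condom, and partner contraception of any kind.
3. The condom is on the list of methods failing in more than 1% per year. Partner contraception has no level.
4. Test the paragraph with two couples:
   - Condom plus an intrauterine device: the paragraph is satisfied, and the device is on the highly effective list. This is consistent with 6a.
   - Condom plus a diaphragm with spermicide: the paragraph is satisfied, but footnote 5 classes the pairing as not highly effective. This falls short of 6a.
5. The paragraph accepts both couples and so does not separate those who meet 6a from those who do not. In Canada the second couple would be stopped by the requirement for one highly effective method.

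**Period**

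- End: the appendix runs to 90 days after the end of systemic exposure, and 6a to 90 days after the last dose. Exposure cannot end before the last dose, so the appendix is not shorter here.
- Start: 6a begins at screening; the condom sentence covers treatment onwards. Screening lasts at most 28 days, and treatment starts within 2 days of randomization (Section 8.1.2). The difference is at most 28 + 2 = 30 days. No itacitinib or placebo is taken in those days.
- Period governed by the instruction: at most 36 months of treatment (Section 6.1.1.6) plus 90 days, or about 36 + 3 = 39 months.

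**Side point for women**

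Bilateral tubal occlusion is on the highly effective list and tubal ligation is on the second list, with no explanation of the difference. Criterion 6c counts only hysterectomy, bilateral oophorectomy or more than 12 months of amenorrhea as nonchildbearing. A woman with ligated tubes must therefore be judged under 6b, and the answer depends on which entry the site reads.

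**The case against.** The strongest reply is that the binding text is already right. Criterion 6a states the level and the period, and it limits what sites communicate to methods that are at least 99% effective. Appendix A waives none of this. Its vasectomy sentence presupposes a requirement for a highly effective method. A site that reads 6a together with footnote 5 would reject the condom-plus-diaphragm couple. All of this stands. It means the defect is one of guidance and that no ineligible couple is formally admitted. It does not close the gap, because the male paragraph is the instruction that 6a tells sites to pass on, and that paragraph does not say which partner methods count. The highly effective list is headed for female participants, and the male paragraph does not refer to it.

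A second reply is that the paragraph prescribes a combination and does not offer the condom alone as the 99% method. This also stands. A reader might infer that the protocol accepts a condom alone for a man whose partner is of child-bearing potential. It does not: the partner is to use contraception as well. Many combinations that follow the paragraph include a highly effective method. The fault is that the paragraph does not require one.

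A third reply is that the documents state no risk from paternal exposure to itacitinib, and that the guidance cited as the appendix's source cannot be consulted here. This is correct, and no such risk is claimed. The point rests on the protocol's own 99% requirement set against the protocol's own classification of methods.

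**Conclusion.** The point holds as a mismatch between an eligibility criterion and the guidance it relies on. Outside Canada, the male paragraph sets no level for partner contraception, so a couple can comply with it and still fall below 6a.

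Two stronger readings are tempting and are not supported. The start difference of up to 30 days might be taken for unprotected exposure, but it precedes any itacitinib or placebo and 6a already covers it, so it is alignment only. The 39 months might be taken for the size of a shortfall, but it is only the longest period that the instruction governs.

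The number of couples affected cannot be estimated, because the documents give no data on sex, age, fertility or contraceptive use. The conclusion assumes only that the 99% in 6a corresponds to the appendix's border of 1% failure per year. There is no effect on the statistical analysis. The change is still worth making, because it is nearly free and concerns the only preventive measure that applies to a male participant's partner.

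**What to change.** At the next amendment, replace the condom and partner sentences in the male paragraph of Appendix A with:

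> From screening through 90 days after the last dose of study drug or the end of relevant systemic exposure, whichever is later, a male participant must either practise sexual abstinence as defined in footnote 4 or use a condom; if he has not had a vasectomy and his partner is of childbearing potential, the partner must also use a method from the highly effective list below.

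Keep the sperm-donation and vasectomy sentences. This gives one start date and one level. It does not oblige an abstinent man to use a condom, and since abstinence is itself on the highly effective list, an abstinent couple needs no further method.

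Optional minor clarification: state how bilateral tubal occlusion and tubal ligation differ, or classify them the same way.

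Cost: a few lines of text, and a few couples may need to change method. Data, analysis and sample size are unaffected.
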